Studies conducted comparing standard drilling (SD) with osseodensification drilling (OD) show significant increase in implant primary and secondary stability with OD. Through surgical compaction of bone into marrow space, OD has been found to increase the insertion torque values regardless of the type of implant surface (machined versus acid-etched implant surfaces).¹ In another study, significantly lower insertion torques have been noted when SD was utilized.² Additionally, through histomorphometric analysis, greater bone-to-implant contact (BIC) and bone area fraction occupancy (BAFO) has been demonstrated with OD.² Autologous bone chips have been recorded with greater frequency in the OD group compared to the SD group.³ The autologous bone chips acted as nucleating surfaces promoting new bone formation resulting in greater implant stability and bone density.³ Another study verified the infrequent presence of bone chips in the SD group compared to the commonly observed presence of bone chips in the OD groups.⁴ When clockwise (CW) and counterclockwise (CCW) OD was compared, higher volume of bone chips was observed in the CCW OD group. Further research has demonstrated increase in ridge dimensions with the OD method. Specifically, narrower ridges measuring 1-3 mm at the crest demonstrated the greatest increase in width accounting for 2.83 ± 0.66 mm increase. Greater changes in ridge width were noted at the crest versus 10 mm from the crest.⁵

Hypothesis:

- Bone Densification protocol does not increase implant primary and secondary stability values in 0-6 wks as compared to standard drilling protocol.
- Bone Densification does not increase ridge dimensions as compared to standard drilling protocol.
- Bone densification does not increase bone volume and density as compared to standard drilling protocol.
- There is no significant difference between bone densification and standard drilling protocols.

Objectives

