- Patient with malignant tumor.
- Patients on daily dose of steroids.
- Patients with history of chemotherapy or radiation for the last 12 months.

Study Procedures

Forty implants will be paired and placed in 20 patients using OsseoDensification (OD) protocol as test, and using standard drilling (SD) protocol as control. Sites will be randomly assigned in comparative patients prior to flap reflection.

Primary Outcome Measures:

All ridge dimensions will be measured immediately after flap reflection and after final osteotomy preparation: at crest, 5 mm and 10 mm apical from the crest. A surgical guide will be fabricated for the implant surgery which will also be marked on the buccal indicating the middle of the osteotomy and the ridge dimensions will be measured using the mark as a standard reference. The measurements will be completed the day of surgery only.

Secondary Outcome Measures:

1. All implants' primary stability will be measured by insertion torque values and by resonance frequency analysis (ISQ) immediately after implant placement (T0). Resonance frequency analysis will be measured at three weeks (T1), six weeks (T2), and twelve weeks (T3) post implant placement.
2. At 6 months all patients will receive CBCT for volumetric analysis.

Digital radiographs (periapical radiographs PA) will be taken prior to implant placement, post placement, and at 6 weeks. Cone beam computer tomography (CBCT) will be obtained prior to implant placement for implant planning and fabrication of a surgical guide, and at 6 months post-implantation for volumetric analysis.

In any incidence of less than 1 mm buccal plate thickness has resulted after bone preparation, bone grafting will be done post implant placement and complete implant coverage will be achieved for two-stage healing protocol. Cases requiring bone grafting will be excluded from the CBCT analysis at 6 months and from 3-week (T1) and 6-week (T2) ISQ readings. Cases requiring two-stage healing will also be excluded from 3-week (T1) and 6-week (T2) ISQ readings, but will be included in 12-week (T3) ISQ readings at second stage surgery.

At 12 weeks all patients will receive dental restorations. Implants' restorative phase will be initiated at any time resonance frequency analysis become equal or more than ISQ 68.

Why 3 weeks, 6 weeks, and 12 weeks ISQ measurements:

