The lowest value of implant stability is at three weeks after implant placement and it is most pronounced in type IV bone. (Barewal et al, Int. JOMI 2003. Sep-Oct; 18 (5) 641-51) Implant Stability increases greatly between week 0 and week 6 and showed slow increase between week 6 and 6 months. (Jae-Min Kim et al, J. Adv. Prosthodont 2009. March; 1 (1) 31-36). Implant stability starts declining after first week and reach its lowest value at three week to start increasing in the fourth week. (Markovic et al, OOOOE 2011. November; 112, (5) 557-63) ISQ is obtained at 12 weeks to ensure implant stability prior to having implants restored.

Data and Safety Monitoring

Implant therapy, either with standard drilling or osseodensification, has some inherent possible complications such as post-operative discomfort, infection, pain, implant failure, swelling and bleeding. All clinical protocols currently in effect in the Graduate Periodontology clinic will be followed in order to minimize these risks. Currently, all patients, undergoing implant therapy at the Graduate Periodontology, receive antibiotics prophylactically, pain medications for management of pain and discomfort, steroids as needed to help with edema, and chlorhexidine mouthrinse to maintain the surgical sites clean as possible by reducing the bacterial load. In the event of implant failure, the implant will be removed, and the site will be grafted for future repeat of the implant therapy at the specific area.

Statistics & Computer tomography analysis

Data will be evaluated with paired T-tests. The total number of subjects enrolled in the study will be twenty and all eligible subjects will be provided with the opportunity to participate. Termination of the trial will be considered only when unexplained implant failures are observed, excluding implant failures associated with systemic conditions, infections or other well documented contributing factors in the literature.

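### A failed implant takes its pair out of the later ISQ comparisons, and failure by technique is not reported, so unequal failures would tilt the T1 to T3 result towards the technique that fails more

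*Combined protocol and SAP*

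**What the plan says.** Study Procedures sets up the pairing: "Forty implants will be paired and placed in 20 patients using OsseoDensification (OD) protocol as test", with standard drilling (SD) as control. The primary outcome is ridge dimension at surgery: "The measurements will be completed the day of surgery only". The secondary outcomes are insertion torque and ISQ at placement (T0), later ISQ, and a 6-month CBCT. On later ISQ the plan says: "Resonance frequency analysis will be measured at three weeks (T1), six weeks (T2), and twelve weeks (T3) post implant placement".

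Statistics & Computer tomography analysis gives one method: "Data will be evaluated with paired T-tests". It has no rule for missing readings. The exclusions from ISQ written under Secondary Outcome Measures concern grafting for a thin buccal plate and two-stage healing, not failure.

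Data and Safety Monitoring names implant failure as a possible complication of either technique and continues: "In the event of implant failure, the implant will be removed, and the site will be grafted for future repeat of the implant therapy". The only other use of failure is the termination rule in the statistics section. That rule applies to the trial as a whole, is triggered by unexplained failures, and leaves out those put down to systemic conditions, infection or other documented factors. Failure or survival by technique does not appear in the Hypothesis, Objectives, Primary Outcome Measures or Secondary Outcome Measures.

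**The concern.** ISQ measures how firmly the implant is held. An implant that fails through loss of stability is the extreme low end of that scale, and removal takes it off the scale altogether. At every later time point the paired t-test then uses only pairs in which both implants are still in place. If one technique loses more implants than the other, its worst results are the ones missing, and the remaining differences look better for it than they should.

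This matters because stability over the first six weeks is the first hypothesis and ISQ to 12 weeks is a stated objective. Without a failure count by technique beside the ISQ result, a reader could not tell similar stability from similar stability among survivors. The Publication Plan intends to pool these results with other centers, and failures that are not tabulated by technique could not be pooled.

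**Working it through.** **The plan's own figure.** 20 patients × 2 implants = 40 implants, which agrees with the plan. The documents give no failure rate, ISQ standard deviation, alpha or power, so everything below rests on stated assumptions.

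**1. Which data are lost.**
- Ridge dimensions, insertion torque and T0 ISQ are taken at surgery. A later failure cannot change them.
- An implant that fails before T1 loses T1, T2 and T3. One that fails between T1 and T2 keeps T1 and loses T2 and T3. One that fails between T2 and T3 loses only T3.
- In each case the partner's reading is lost as well, because a paired t-test needs both.

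**2. Size and direction of the shift.** Assume no true difference in ISQ, both implants normally distributed with standard deviation s and within-patient correlation r, and failure of the lowest fraction f of one technique's implants, with none in the other.

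The mean of the surviving implants rises by s × h, where h = φ(z_f)/(1 − f), φ is the standard normal density and z_f the lower f quantile. The partners in the retained pairs rise by r × s × h. The complete-pair difference therefore shifts by s × (1 − r) × h towards the failing technique.

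| f | h | smallest (s = 5, r = 0.6) | largest (s = 8, r = 0.3) |
|---|---|---|---|
| 5% | 0.1031/0.95 = 0.109 | 5 × 0.4 × 0.109 = 0.2 | 8 × 0.7 × 0.109 = 0.6 |
| 10% | 0.1755/0.90 = 0.195 | 5 × 0.4 × 0.195 = 0.4 | 8 × 0.7 × 0.195 = 1.1 |
| 15% | 0.2332/0.85 = 0.274 | 5 × 0.4 × 0.274 = 0.5 | 8 × 0.7 × 0.274 = 1.5 |

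A simulation of the same set-up gives the same values to within 0.02 ISQ (its smallest value at 15% is 0.55, hence about 0.6 elsewhere in this note). Comparing all surviving implants unpaired would shift by s × h, about 0.5 to 2.2 over the same range, so pairing reduces the bias but does not remove it. With failures at 10% in one technique and 5% in the other, the simulated shift is 0.2 to 0.5. With equal rates it is zero by symmetry.

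**3. How often a pair is lost.** With failure rates a and b, assumed independent, the expected number of complete pairs is 20(1 − a)(1 − b), and the chance of losing at least one is 1 − [(1 − a)(1 − b)]^20.
- 5% and 2%: 20 × 0.95 × 0.98 = 18.6 pairs; chance 0.76.
- 10% and 2%: 20 × 0.90 × 0.98 = 17.6 pairs; chance 0.92.

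**4. Precision.** At two-sided 5% (assumed), the standardised paired difference detectable with 80% power rises from 0.66 with 20 pairs to 0.70 with 18 and 0.75 with 16. This is a minor cost beside the bias.

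**5. Can failure itself be tested?** With k discordant pairs all in one direction, the exact McNemar p-value is 2 × 0.5^k: 0.0625 at k = 5 and 0.031 at k = 6. At least six one-sided discordant pairs out of 20 would be needed. With no failures in 20 implants, the one-sided 95% upper limit is 1 − 0.05^(1/20) = 13.9%. Failure can be described here, but not tested with useful power.

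**The case against.** **The reach is narrow.** The primary outcome, insertion torque and T0 ISQ cannot be affected, and the stability hypothesis runs only to six weeks. This stands. The point concerns secondary time points.

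**Pairing protects the comparison.** Both techniques are compared on the same complete pairs, so it is not true that one is judged on its survivors while the other keeps all its implants. This stands in part: the shift is smaller than in an unpaired comparison, but has the same direction.

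**Failures will be known anyway.** The termination rule requires failures to be noticed and their cause judged, and technique is traceable because each patient has one site of each. This also stands in part. The information can be recovered, but nothing commits the trial to reporting it by technique, and the rule sets explained failures aside.

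**The effect may be small.** This stands. The ranges above put every failure in one technique's weakest implants; similar rates would largely cancel. Nor would the supporting analysis readily overturn a clear result. In 20 pairs, two failures ranked worst give an adverse rank sum of 20 + 19 = 39. If the other 18 differences all pointed the opposite way, that is below the two-sided 5% critical value of 52, and the result would remain significant.

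**Stronger readings that the documents do not support.**
- A reader might infer that removing failures would hide a real reversal in ISQ. That depends on invented values for the failed implants and the failure split, and the documents supply neither.
- A reader might infer that nothing is observed after restoration, because the plan says "Digital radiographs (periapical radiographs PA) will be taken prior to implant placement, post placement, and at 6 weeks" and the last ISQ is at 12 weeks. But Secondary Outcome Measures also lets the restorative phase start whenever ISQ reaches 68, so some of these readings may follow it. That sentence and the 12-week restoration sentence beside it need to be reconciled. The 6-month scan ("At 6 months all patients will receive CBCT for volumetric analysis") would also show whether an implant is present.
- A reader might infer that the fourth hypothesis ("There is no significant difference between bone densification and standard drilling protocols") will be reported as overall equivalence. It has no outcome or test attached, so that is conjecture.

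**Conclusion.** The point holds for ISQ at T1, T2 and T3. The plan removes failed implants, uses an analysis that then drops their pairs, and does not report failure by technique. If failures are unequal and tied to low stability, the comparison is biased towards the technique with more of them.

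Under the stated assumptions (SD 5 to 8, correlation 0.3 to 0.6, all failures in one technique's lowest-ISQ implants) the shift is about 0.2 to 0.6 ISQ at 5% failures and 0.6 to 1.5 at 15%. It is near zero at similar rates. The true size cannot be known from the documents. The direction follows from the design, and the correction is cheap, so it should be made before analysis.

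**What to change.** 1. Record implant failure (yes/no, with date) for all 40 implants at the existing T1, T2, T3 and 6-month CBCT visits, including grafted and two-stage sites and including failures judged to be explained.
2. List failure by technique as a descriptive secondary safety outcome, reported as paired counts: neither implant failed, osseodensification only, standard drilling only, both. Do not plan a formal test.
3. For ISQ at T1 to T3, keep the paired t-test on complete pairs, and state beside each result how many pairs were lost to failure, by technique.
4. Add a supporting signed-rank comparison at each of these time points. Keep every pair otherwise eligible then, and rank a failed implant as the worst outcome. Fix the handling of ties in advance, for example several failed pairs sharing the largest ranks and a pair with both implants failed counting as no difference.

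The cost is a short amendment, one field per implant at visits already scheduled, and one added analysis. No treatment, visit or primary analysis changes. The downside is that the supporting result is in ranks, so it shows whether the conclusion is robust but gives no difference in ISQ units.

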The aim of this study is to compare ridge dimensional changes between densification and standard drilling protocols. Additionally, primary and secondary stability of implants placed by bone densification and standard drilling protocols will be compared. A comparison of the insertion torque values (measured in Ncm) and temporal (immediate, 3, 6, and 12 weeks) implant stability quotients at osteotomies prepared with standard drilling procedures or when subjected to osseodensification surgical instrumentation will be performed. Dimensional changes will be measured before and after completion of the implant osteotomy, and compared between standard and osseodensification surgical instrumentation. Finally, volumetric changes and ridge dimensional changes will be evaluated between initial CBCT and 6 months follow-up CBCT.

Study Design

Twenty patients (we will try to balance male and female population sample if it is possible) in need to receive at least 2 dental implants in single-unit or larger span edentulous spaces will be selected. Nonsmoking and not systemically compromised patients will be selected. The following scenarios will be chosen to rehabilitate the anterior and posterior regions in this study.

- **If maxilla:**
 - split-mouth, implant insertion to replace anterior or posterior teeth: one side will receive osseodensification drilling instrumentation and the other standard drilling. Site selection is randomized by coin toss.
 - same side, adjacent teeth: Site selection will be randomized by coin toss.
- **If mandible:**
 - split-mouth or same side surgical instrumentations will be performed, as described for maxilla.

Surgical technique

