Final implant (NobelReplace® Conical) and respective bur diameter for either osseodensification instrumentation and conventional drilling will be either 3.5 mm, 4.3 mm or 5.0 mm. Implant lengths will be from 8.0 up to 13.0 mm. Versah (Fig. 2) and NobelReplace ® Conical implant surgical kit (Fig. 1) present burs with identical diameter and instrumentation will be performed so last bur diameter matches with chosen implant diameter. When using Versah, counterclockwise drilling will be performed in maxilla, and in mandible clockwise drilling. Before surgery, all patients will receive intraoral scans and will be subjected to tomographic examination of the edentulous site for virtual implant planning, surgical planning, implant selection, and fabrication of a surgical guide with a mark on the buccal aspect identifying the middle of the osteotomy. The osseodensification technique will be used for comparison with conventional drilling regarding ridge dimensional changes measured with a ridge caliber (Krekler Sliding Caliper Round Gauge Dental Instrument) at

implantation (T0); and insertion torque (IT) values and implant stability quotients (ISQ) at implantation (T0), 3 (T1,) 6 (T2), and at 12 weeks (T3). ISQ will be measured with Osstell ISQ meter. Data will be evaluated with paired t-tests. After T0, patients will receive a healing abutment which will be removed and repositioned for T1, T2, and T3 evaluations. After 12 weeks patients will be prosthetically restored if insertion torque was 35 Ncm and/or ISQ values are 68. After 6 months, follow-up tomographic examination will be completed for volumetric analysis.

Study Population

Patients of the Graduate Periodontology clinic requiring implant therapy will be screened and selected to participate in the study based on the following inclusion and exclusion criteria:

Inclusion Criteria

- Adults aged 22 years and older.
- Patients who understand and agree to this study.
- Adequate Oral hygiene
- One or more edentulous spaces, which are 10 weeks or longer after extractions
- Patients requiring signature from a Legally Authorized Representative (LAR) will be eligible to participate in the study

Exclusion criteria:

- Grafted extraction socket or ridge augmentation procedure utilizing xenogenic bone graft material.
- Pregnancy as checked via medical history
- Smoking of more than 5 cigarettes/day.
- History of alcoholism or drug abuse during the last 5 years.
- Uncontrolled Hypertension or diabetes.

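### Should baseline ridge width be a covariate in the primary comparison, and not only be subtracted?

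*Combined protocol and SAP*

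**What the plan says.** The method is named twice, without a covariate: "Data will be evaluated with paired t-tests" under Surgical technique, and "Data will be evaluated with paired T-tests" under Statistics & Computer tomography analysis. Neither place says which two quantities form the pair. Two other sections supply this. The ridge null hypothesis is "Bone Densification does not increase ridge dimensions as compared to standard drilling protocol" (Hypothesis), and the Objectives state: "Dimensional changes will be measured before and after completion of the implant osteotomy, and compared between standard and osseodensification surgical instrumentation". Together they point to the change under osseodensification against the change under standard drilling, within patient.

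Under Primary Outcome Measures, "All ridge dimensions will be measured immediately after flap reflection and after final osteotomy preparation", at the crest and at 5 mm and 10 mm below it. Study Procedures plans 40 implants as 20 pairs and adds: "Sites will be randomly assigned in comparative patients prior to flap reflection". The caliper baseline is therefore read after allocation but before drilling. Study Design allocates by coin toss, also for neighbouring sites ("same side, adjacent teeth: Site selection will be randomized by coin toss"), and has no rule to match paired sites on width.

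Background Information reports that, with osseodensification, ridges 1-3 mm wide at the crest gained most (2.83 ± 0.66 mm), and that width changed more at the crest than 10 mm from it. It gives no slope, and no gradient for standard drilling.

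**The concern.** A baseline covariate exists for every site and level at no extra cost, the sponsor's own background suggests that starting width matters, and paired sites need not be equally wide. A simple change score fixes the coefficient of baseline at one, whereas a regression would estimate it. With 20 pairs and no stated power calculation, any avoidable noise counts. If change depended on width in the same way under both techniques, a chance difference in mean width between the two sets of sites would shift the estimate, and adjustment would remove that shift. At stake would be the power of the primary comparison, not its validity.

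**Working it through.** **Inputs.** From the documents: 20 pairs, coin-toss allocation within patient, paired t-tests, width read before drilling. The plan gives no significance level, power, effect size or standard deviation, so there is no figure of its own to reproduce. Assumed: two-sided 5%; standard deviation of width σ = 1.0 or 1.5 mm; within-patient correlation of width c = 0.5 or 0.8; residual standard deviation 0.5 mm per site; true difference 0.4 mm; slope b of 0.2, 0.3 or 0.4 mm less change per mm of width.

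**Step 1: validity.** The coin toss decides which site gets which technique, so the mean paired difference in change is unbiased whatever the baseline widths. Simulated type I error is 0.049-0.052 for both the paired t-test and the adjusted analysis.

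**Step 2: break-even.** The adjusted analysis regresses the paired difference in change on the paired difference in baseline, and its intercept is the treatment effect. Its variance relative to the paired t-test is (1 - ρ²)(1 + 1/(n - 3)), where ρ is the correlation between the two differences. With n = 20 the factor is 1 + 1/17 = 18/17 = 1.059. Break-even is 1 - ρ² = 17/18, so |ρ| = √(1/18) = 0.236. For an effect at which the paired t-test has 80% power, adjusted power is 77.5% at ρ = 0, about 80% at 0.25 and 88% at 0.5.

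**Step 3: the documented case, a width slope under osseodensification only.** The variance of the paired difference in change is b²σ² + 2(0.5²) = b²σ² + 0.5. The variance of the baseline difference is 2σ²(1 - c), and the covariance has size bσ²(1 - c). Hence

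ρ² = [(1 - c)/2] × b²σ² / (b²σ² + 0.5).

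The first factor is the share of width-related variance that the baseline difference can explain: 25% at c = 0.5 and 10% at c = 0.8. The rest lies in the pair's mean width, which this covariate does not touch. Example: b = 0.4, σ = 1.5, c = 0.5 gives b²σ² = 0.36 and ρ² = 0.25 × 0.36/0.86 = 0.105, so |ρ| = 0.323.

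Power comes from simulation, 40,000 trials per setting:

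| σ (mm) | c | b | \|ρ\| by formula | Power unadjusted / adjusted (%) | Change (points) |
|---|---|---|---|---|---|
| 1.5 | 0.5 | 0.2 | 0.195 | 59.5 / 58.7 | -0.8 |
| 1.5 | 0.5 | 0.3 | 0.268 | 52.5 / 53.2 | +0.7 |
| 1.5 | 0.5 | 0.4 | 0.323 | 44.9 / 46.8 | +1.9 |
| 1.0 | 0.5 | 0.2 | 0.136 | 63.9 / 62.0 | -1.9 |
| 1.0 | 0.5 | 0.3 | 0.195 | 59.9 / 58.9 | -1.0 |
| 1.0 | 0.5 | 0.4 | 0.246 | 55.6 / 55.8 | +0.2 |
| 1.5 | 0.8 | 0.2 | 0.124 | 59.9 / 58.0 | -1.9 |
| 1.5 | 0.8 | 0.3 | 0.170 | 52.7 / 51.3 | -1.4 |
| 1.5 | 0.8 | 0.4 | 0.205 | 44.4 / 43.9 | -0.5 |
| 1.0 | 0.8 | 0.2 | 0.086 | 64.0 / 61.8 | -2.2 |
| 1.0 | 0.8 | 0.3 | 0.124 | 59.8 / 58.0 | -1.8 |
| 1.0 | 0.8 | 0.4 | 0.156 | 55.0 / 53.8 | -1.2 |

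Three settings exceed 0.236, and they are the three that gain. The other nine lose.

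**Step 4: the other cases.**

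- Width irrelevant: adjustment costs 2.3 to 2.5 points (for example 66.9 / 64.4%). The documents report no gradient at 5 mm or 10 mm, so this case is quite possible there.
- Half the slope under standard drilling: -1.8 (65.5 / 63.7%) to +10.0 (49.1 / 59.1%).
- The same slope under both techniques: -1.1 (66.0 / 64.9%) to +19.6 (45.0 / 64.6%).

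The last two need a slope under standard drilling, which the documents do not report.

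**Step 5: the same question through the pre-post correlation r.** If the paired differences in width before and after drilling have equal standard deviations, the variance ratio is [(1 + r)/2] × 18/17. This is 0.79 at r = 0.5, 0.95 at 0.8, 1.01 at 0.9 and 1.03 at 0.95. The documents do not give r.

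**The case for a change.** The best case for adjusting is that the stakes are lopsided: a loss of at most about 3 points against a possible gain of about 20, for one degree of freedom (19 to 18) and a few sentences. Caliper error strengthens it. Random error in the baseline reading is subtracted under both techniques, so it acts like a common slope. With an osseodensification-only slope of 0.3 and an assumed reading error of 0.1, 0.2 or 0.3 mm, the change in power is -1.4 to +0.9, +0.3 to +2.0 and +3.5 to +5.2 points. The table in the working assumes no such separate error, so its nine losses are not a firm forecast. Reading the baseline after allocation is no bar either, since drilling cannot alter a width measured before it.

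This makes adjustment defensible, but it does not make its absence a weakness. The lopsidedness comes from scenarios without support in the documents, and no repeatability figure for the caliper is given. The fitted slope would also be hard to read: "instrumentation will be performed so last bur diameter matches with chosen implant diameter", so implant and bur size may vary with ridge width.

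It is also true that the statistics section does not name the paired quantity. The hypothesis and the objectives leave little doubt about it, and naming it outright does not depend on any argument about a covariate.

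**Conclusion.** The concern does not hold. The planned paired t-test on change is valid and unbiased under within-patient randomisation, and no improvement from a baseline covariate is demonstrated. In the one situation that the documents describe, adjustment changes power by between -2.2 and +1.9 points, if baseline reading error is ignored. Over all assumed settings the range is about -3 to +20 points, and the upper end depends on a width slope under standard drilling that no section reports. These sizes rest on assumed values for the width standard deviation, within-patient correlation, residual standard deviation, slopes and true difference. The break-even of about 0.24 depends only on the 20 pairs. With so few pairs, the choice between a paired t-test and a one-covariate regression at all three levels is a matter of judgement, and the plan's choice can stand.

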Implant Primary Stability and Ridge Dimensional Changes Utilizing the Osseodensification Protocol

NCT05283928

Version Date: 09/12/2023

| | |
|--------------------------------|--|
| Protocol Title: | Implant Primary Stability and Ridge Dimensional Changes Utilizing the Osseodensification Protocol |
| Principal Investigator: | [name] DDS, MS |
| Co-Investigators: | [name] DDS, MS, PhD, [name], BDS, DSc, MDS, [name] DDS, MS, DMSc, [name] |
| Study Coordinator: | [name] and [name] |
| Population: | Twenty patients, 22 years or older, that are not systemically compromised and nonsmoking. |
| Number of Sites: | One |
| Study Duration: | 24 weeks |
| Subject Duration: | 24 weeks |

General Information

Implant stability is critical for the success of osseointegration and for immediate loading protocols. Surgical instrumentation techniques, implant macrogeometric design, bone quantity and quality all affect implant primary stability. In contrast to standard drilling for implant placement, osseodensification drilling compacts and auto-grafts bone at the osteotomy walls resulting in increase of ridge dimension, higher insertion torque, and in increased temporal bone to implant contact even in low density bone.

Background Information

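### The only termination trigger leaves out infection-associated implant failures by name, and no all-cause tally of failures by drilling technique is described, so a technique-related excess could miss the trigger

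*Combined protocol and SAP*

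**What the plan says.** The termination rule is one sentence in the Statistics & Computer tomography analysis section: "Termination of the trial will be considered only when unexplained implant failures are observed, excluding implant failures associated with systemic conditions, infections or other" documented factors. The carve-out reads in full "excluding implant failures associated with systemic conditions, infections or other well documented contributing factors in the literature". The rule gives no number or rate of failures and no comparison between techniques. It does not define what makes a failure unexplained or say who decides.

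The Data and Safety Monitoring section says that implant therapy, by either technique, "has some inherent possible complications such as post-operative discomfort, infection, pain, implant failure, swelling and bleeding". On a failed implant it says "In the event of implant failure, the implant will be removed, and the site will be grafted", and it describes no step for entering the event against the technique used at that site.

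General Information supplies the background on stability: "Surgical instrumentation techniques, implant macrogeometric design, bone quantity and quality all affect implant primary stability", and "Implant stability is critical for the success of osseointegration and for immediate loading protocols".

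Study Procedures sets the numbers: "Forty implants will be paired and placed in 20 patients using OsseoDensification (OD) protocol as test", with standard drilling as control. Implant failure is neither a primary nor a secondary outcome there, and the paired t-test is the only test named in the document.

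**The concern.** The trial compares two ways of preparing the implant site. The safety event most relevant to that comparison is an implant failure that happens more often with one technique. The rule sorts failures by presumed cause before they can prompt a review, and one of the causes it removes, infection, is a complication the protocol itself expects with either technique. If one technique led to more infections and so to more failures, each of those failures would have a named, excluded cause.

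The open-ended third category widens the exclusion. The protocol treats the effect of instrumentation on stability, and the importance of stability for osseointegration, as established. An investigator could therefore class a low-stability failure as having a documented contributing factor. Cause is assigned after the event, and neither a definition nor an assessor unaware of technique is described.

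At stake is whether the one stated trigger would respond to a one-sided run of failures while patients are still being treated, and whether failures could be reported by technique at the end in a consistent way.

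**Working it through.** **Step 1: the provisions side by side.**

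| Question | What the document gives |
|---|---|
| What may prompt consideration of termination? | Unexplained implant failures only |
| What is removed from that count? | Failures associated with infection, systemic conditions or other documented factors |
| Is infection expected with the techniques under study? | Yes, listed for either technique, as is implant failure |
| Is low stability named as an excluded cause? | No; it could fall under the third category |
| Is there another trigger, a tally by technique, or an analysis of failures? | None described |

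The infection exclusion is therefore explicit. The low-stability exclusion is a possible reading. The systemic exclusion matters least for the comparison, because both sites of a pair are in the same patient.

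**Step 2: how much the exclusion could remove.** The plan gives no failure rate or boundary, so there is no planned figure to reproduce. Inputs:

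- n = 20 implants per technique (40 implants, 20 patients, one of each technique per pair; 40 / 2 = 20).
- p = true failure risk in one technique. Assumed; 5%, 10% and 15% shown.
- e = share of failures classed as explained. Assumed; 0, 50% and 80% shown.

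Treating implants of one technique as independent, the risk of a counted failure is q = p × (1 − e). Then:

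- P(at least one counted) = 1 − (1 − q)^20
- P(at least two counted) = 1 − (1 − q)^20 − 20 × q × (1 − q)^19

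For p = 10%:

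- e = 0, q = 0.10: 1 − 0.9^20 = 0.878; at least two, 0.608.
- e = 50%, q = 0.05: 1 − 0.95^20 = 0.642; at least two, 0.264.
- e = 80%, q = 0.02: 1 − 0.98^20 = 0.332; at least two, 0.060.

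| True risk | Counted failures | All count | Half explained | 80% explained |
|---|---|---|---|---|
| 5% | at least 1 | 64% | 40% | 18% |
| 5% | at least 2 | 26% | 9% | 2% |
| 10% | at least 1 | 88% | 64% | 33% |
| 10% | at least 2 | 61% | 26% | 6% |
| 15% | at least 1 | 96% | 79% | 46% |
| 15% | at least 2 | 82% | 45% | 12% |

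Both thresholds are shown because the rule states no number. If every failure were classed as explained, the chance would be zero at any risk.

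**Step 3: a lopsided result.** Suppose all failures fall in one technique. The chance that none of k failures counts is e^k.

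- Three failures against none: 0.5^3 = 13%; 0.8^3 = 51%.
- Six failures against none: 0.5^6 = 2%; 0.8^6 = 26%.

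The two-sided exact sign test on discordant pairs gives 2 × 0.5^6 = 0.031 for six against none and 2 × 0.5^5 = 0.063 for five against none. Formal evidence of a difference would thus need a very one-sided result, which makes complete counting more useful here than a formal boundary.

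**The case against.** Several points on the other side stand.

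- **The rule does not exclude every technique-related failure.** An uninfected implant that fails to integrate for no identified reason still counts. A reader might infer that the exclusions cover all the ways a technique could cause failure. The document lists no such mechanisms, so this cannot be said.
- **Low stability is not named.** Torque and ISQ are trial outcomes, so an investigator might treat a low-stability failure as exactly the signal sought. Only the weaker statement holds: such a failure could be classed as explained.
- **Failures may well be recorded.** A reader might infer that they go unrecorded or that no visit would reveal an infection. The document does not support this. Study data go into a spreadsheet, the healing abutment is removed at 3, 6 and 12 weeks in one-stage cases, and periapical films are taken at 6 weeks. What is missing is a stated failure or infection field by site, and a use for it.
- **The illustration rests on assumed inputs.** Neither the risks nor the explained shares have a source, and the calculation covers one technique's 20 implants while the rule covers all 40. With a threshold of one and half of failures explained, the loss is moderate.
- **The primary result is not touched.** Ridge dimensions are measured on the day of surgery, and 20 pairs give little formal power on failures in any case. If the stated 24 weeks for both study and subject duration are taken literally, few patients would come later to be protected.
- **Stopping is a sponsor and investigator decision.** That is so, and the remedy leaves it with them.

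None of this answers the central point. Infection-associated failures are excluded by name, infection is an expected complication of the techniques being compared, and nothing else in the document is described as catching an imbalance.

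**Conclusion.** The point holds for the termination trigger. As written, a technique-related excess of failures through infection is excluded by name, and one through low stability could be. No other trigger and no tally or analysis of failures by technique is described.

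The size depends on unknowns. At an assumed 10% risk in one technique, the chance of at least one counted failure falls from 88% to 64% or 33% as the explained share goes from none to 50% or 80%. For at least two it falls from 61% to 26% or 6%. These figures assume independent implants within a technique and show the direction and possible scale only.

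This should be fixed because it is cheap and concerns the only stated trigger. It does not threaten the primary comparison. A reader might go further and conclude that the trial is blind to harm from either technique; the text does not support that, since failures without an identified cause still reach the trigger.

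**What to change.** Amend the termination paragraph and the Data and Safety Monitoring section as follows.

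1. Record every implant failure as it occurs, by patient and by technique (OD or SD), whatever its cause.
2. Keep suspected cause (infection, low torque or ISQ, systemic, none identified) as a descriptive field. It informs the review but is not a condition for entering the count. Where feasible, have cause judged by someone unaware of the technique used at the site.
3. Let the all-cause table by technique, together with the other complications the protocol already names, prompt the review of whether to continue. Report the same table at the end of the trial.

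The threshold for calling a review, and every decision on continuation, stay with the sponsor and investigator.

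The cost is a one-paragraph amendment and a few columns in the existing spreadsheet. The small downside is an occasional review of a failure later judged unrelated to technique.
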